16.1.4.5. Evaluate the Association between Amyloid Reduction and Treatment Exposure

The total treatment exposure at each visit, defined as the cumulative OLE dose prior to the start of the associated visit, will be calculated for each subject. Linear mixed effects model will be used to estimate the association between amyloid reduction and the treatment exposure.

The change from baseline in PiB-PET SUVR will be the dependent variable and the total treatment exposure at each visit and the baseline PiB-PET SUVR will be independent variable. Random effects in intercept and total treatment exposure will be included in the model to account the correlation among the repeated measures. This analysis will be applied to the OLE Gant mITT population and will also be run with baseline covariates such as disease status (asymptomatic vs symptomatic) and EYO. When the disease status is included in the model, the interaction between disease status and total treatment exposure will also be included so that the treatment effect will be evaluated separately for each disease status.

Figures of individual amyloid removal vs individual total dose exposure will be presented as deemed necessary by Washington University team and may be included in CSR as needed. If the plot demonstrates a non-linear relationship, an ad-hoc non-linear mixed effects model will be used to estimate this non-linear relationship.

Figures of model estimated mean over time by high dose and low dose or spaghetti plots of

Author: [REDACTED]

Version Number:

7

Version Date:

07Dec2023

Template No.: CS_TP_BS016 Revision 6

Reference: CS_WI_BS005

Effective Date: 02Dec2019

individual data over time/EYO by high dose and low dose will be presented as deemed necessary by Washington University team and may be included in CSR as needed.

16.2. SECONDARY EFFICACY

For details of the collection methods for each test please refer to the protocol. For each secondary efficacy variable, the direction of benefit with effective drug is listed below. These may be calculated as change from baseline or difference between drug vs. control.

16.2.1. SECONDARY EFFICACY VARIABLES & DERIVATIONS

16.2.1.1. Key Secondary Efficacy Variables

- Clinical Dementia Rating – Sum of Boxes (CDR-SB): Higher scores indicate worse performance.
- CDR Global: Higher scores indicate worse performance.
- DIAN-TU OLE Cognitive Composite (OLE Cognitive Composite)

Based on the four components, the DIAN-TU-001 OLE Cognitive Composite will be calculated using the following formula: $Y = (0.25) \frac{M-mean}{SD} + (0.25) \frac{W-mean}{SD} + (0.25) \frac{A-mean}{SD} + (0.25) \frac{D-mean}{SD}$, where, D represents the WMS-R Digit Span Backward Recall, A represents the Category Fluency (Animals) value, W represents the Wechsler Adult Intelligence Scale Digit Symbol Substitution Test value, and M represents the Mini Mental State Examination value. The mean (SD) for each of the four parameters will be calculated using the double-blind baseline data of the mutation positive subjects in the DIAN-TU-001 trial. Lower scores of each component indicate worse performance.

- Functional Assessment Scale (FAS): Higher scores indicate worse performance.
- Mini-Mental State Examination (MMSE): Lower scores indicate worse

Author: [REDACTED]

Version Number:

7

Version Date:

07Dec2023

Template No.: CS_TP_BS016 Revision 6

Reference: CS_WI_BS005

Effective Date: 02Dec2019

performance.

- Tau PET Binding Partial Volume Corrected Standardized Uptake Value Ratio - Parietal Composite (Tau PET SUVR): The summary region is the average SUVR values for the postcentral gyrus, supramarginal gyrus, superior parietal cortex, inferior parietal cortex, precuneus, posterior cingulate, and isthmus cingulate regions. Expected to decrease with effective drug.
- CSF pTau181: Expected to decrease with effective drug.
- CSF NFL: Expected to decrease with effective drug.
- CSF Amyloid Beta1-42/40: Expected to increase with effective drug

16.2.2. MISSING DATA METHODS FOR SECONDARY EFFICACY VARIABLE(S)

Missing values in the clinical or cognitive assessments (such as MMSE, FAS etc.) are expected to be rare. If at any given visit, the number of missing items within a questionnaire is less than 30% of the total number of items, then the score for this component at this visit will be calculated as the sum of the non-missing items multiplied by the ratio of the total number of items to the number of the non-missing items (Doody, 2014). If the number of missing items is equal to or greater than 30%, then the score at this visit is considered missing (Doody, 2014).

If at any given visit, where all four components of the OLE Cognitive Composite are intended to be measured and one of the four components has missing scores, meaning less than 30% of the total components as described above, then the OLE Cognitive Composite will be calculated using only the other three components and with the method described in SAP [Section 16.2.1.1](#). But the composite will be weighed by 1/3 instead of 0.25. If two or more components have missing scores, then the composite will be considered missing as well.

[REDACTED] [REDACTED]

Author: [REDACTED]

Version Number:

7

Version Date:

07Dec2023

Template No.: CS_TP_BS016 Revision 6

Reference: CS_WI_BS005

Effective Date: 02Dec2019

If at any given visit, only some of the four components are intended to be measured instead of all, then the composite score will not be calculated and will not be used in the analysis for these visits.

Values captured within the FAS as ‘not applicable (e.g., never did)’ (NA) will be treated as missing.

16.2.3. PRIMARY ANALYSIS OF KEY SECONDARY EFFICACY VARIABLES

16.2.3.1. Primary Analysis of CDR-SB

The primary analysis will be on the All Gant Exposure mITT, with other baseline covariates (such as baseline EYO) defined in the same way as baseline for the associated population. The recurrent progression is defined as any progression which is either the first increase in CDR-SB above baseline or any progression above the highest preceding post-baseline value identified as a progression, where progression above the preceding value must be observed at two consecutive measurements unless the progression occurs at the last measurement. Subjects without a progression event at their last measurement will be censored at the time of that measurement. The time-to-event is the time elapse between the two visits where the recurrent progression is observed, or the time since the baseline assessment for the first progression. Subjects can contribute multiple records to the analysis (i.e., once for each progression and potentially for censoring at the time of last measurement). The same definition will be applied to all controls as defined in [Section 5.4](#). The Cox proportional hazards model employing the Andersen-Gill method (Prentice RL, 1981) with robust variance estimator will be used to compare the hazards of recurrent progression in CDR-SB between population and all controls. The model will include treatment group and baseline EYO as the fixed effects. Should the model produce a two-sided p-value less than 0.10, a sensitivity analysis will be conducted using the shared frailty method (add reference).

Author: [REDACTED]

Version Number:

7

Version Date:

07Dec2023

Template No.: CS_TP_BS016 Revision 6

Reference: CS_WI_BS005

Effective Date: 02Dec2019

Analyses will be conducted separately for baseline asymptomatic and symptomatic subjects.

The same analysis will be applied to the OLE Gant mITT population and the OLE Gant All Gant exposure mITT populations, along with all controls. The analysis will also be conducted for each of the three mITT populations based on the baseline asymptomatic and symptomatic subjects presented separately. A Kaplan-Meier figure will be generated for baseline asymptomatic subjects for all three mITT populations and associated controls.

The spaghetti plots of individual data will be presented over time since baseline and over EYO for both the OLE Gant All Gant exposure mITT population and for all controls. These figures, including those described for CDR-SB in Section 3 of the Addendum to the Statistical Analysis Plan created by Washington University prior to the interim analysis, will be generated by Washington University team and may be included in CSR as needed.

16.2.3.2. Primary Analysis of CDR Global

The primary analysis will be on the All Gant Exposure mITT, with all the other baseline covariates (such as baseline EYO) defined in the same way as baseline for the associated population. The time to the first disease progression is defined as the time from the baseline to the first visit where CDR Global is greater than CDR Global baseline value, where a progression is considered an increase above baseline observed at two consecutive measurements unless the progression occurs at the last measurement. Subject without progression will be censored at their last measurement.

The Cox proportional hazards model will be applied to compare the hazards of disease progression in CDR Global between each of the three mITT population separately and all

Author: [REDACTED]

Version Number:

7

Version Date:

07Dec2023

Template No.: CS_TP_BS016 Revision 6

Reference: CS_WI_BS005

Effective Date: 02Dec2019

controls. The models will include the treatment group (specifically gantenerumab and controls) and baseline EYO as the fixed effects.

Analyses will be conducted separately for baseline asymptomatic and symptomatic subjects. A Kaplan-Meier figure will be generated for baseline asymptomatic subjects for all three mITT populations and associated controls.

Spaghetti plot of EYO for each participant will be presented for each of the three mITT populations. Lines and data points will be coded by different color/symbol for different CDR groups (without progression, with progression) and doses. This figure will be generated by Washington University team.

16.2.3.3. Primary Analysis of OLE Cognitive Composite, FAS, MMSE, Tau-PET SUV, CSF NfL and CSF MTBR243

The annual disease progression between the OLE Gant mITT population and all controls (with the exception of internal controls only for Tau-PET SUV) will be compared using a linear mixed effects (LME) model. CSF NfL will be log transformed for the analysis. The LME model will include time since baseline (in years: treated as continuous), treatment group (the OLE Gant mITT and all control), interaction between the treatment group and time, and random intercepts and slopes for each subject as the random effects. The unstructured covariance will be used to model the covariance between random intercepts and random slopes and will be modelled separately for baseline asymptomatic and symptomatic subjects.

The same analysis will also be applied to the OLE Gant All Gant exposure mITT population and the All Gant exposure mITT populations, along with all controls. This model will be tested using linear splines, which fits two slopes with one prior to the OLE baseline and one after the OLE

Author:	[REDACTED]	Version Number:	7
	[REDACTED]	Version Date:	07Dec2023
Template No.:	CS_TP_BS016 Revision 6	Reference:	CS_WI_BS005
Effective Date:	02Dec2019		

Copyright © 2009, 2010, 2012, 2016, 2018, 2019 [REDACTED] All rights reserved. The contents of this document are confidential and proprietary to [REDACTED] Holdings Inc. and its subsidiaries. Unauthorized use, disclosure or reproduction is strictly prohibited.

baseline (the linear splines have a node at the OLE baseline) to account for the different dosing regimens in the DIAN-TU-001 gantenerumab exposure population; for the pooled controls, only one slope will be fitted since no treatment was administered at any point in time. The analysis will also be conducted for each population based on the baseline asymptomatic and symptomatic subjects presented separately.

Figures of model estimated mean over time by treatment arms or spaghetti plots of individual data over time/EYO by treatment arms will be presented as deemed necessary by Washington University team and may be included in CSR as needed. The plots will also be presented separately for baseline asymptomatic and symptomatic subjects at the OLE baseline.

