3. All Gant exposure mITT: Any subjects treated with Gantenerumab in either DB or OLE who meet mITT criteria using the baseline associated with the first period of Gantenerumab exposure as the baseline reference point. Refer to figure below where the data contributing to the population is highlighted in yellow (and denoted with 'Tx') any period of planned gantenerumab treatment, regardless of double-blind treatment, with controls (further described in [Section 5.4](#)) highlighted in green from both placebo double-

Author: [REDACTED]

Version Number:

7

Version Date:

[figure not shown]
07Dec2023

Template No.: CS_TP_BS016 Revision 6

Reference: CS_WI_BS005

Effective Date: 02Dec2019

blind only subjects and matched controls from DIAN-OBS.

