5.4. GROUPS OF CONTROLS

To facilitate the analysis, several groups of controls will be defined. It is acknowledged that data for the vast majority of subjects in the controls will represent a shorter duration than seen in subjects within OLE Gant All Gant exposure mITT.

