5.4.3. MAIN SET CONTROLS

The main set controls are defined as the external controls plus the internal set controls.

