17. SUBSET OF ANALYSES AT THE INTERIM

The two objectives of the interim analysis are to determine if gantenerumab OLE treatment results in clinical benefit and determine the extent of amyloid removal compared to the double-blind period. The primary analyses for the interim will be the primary analysis of CDR Global

Author: [REDACTED]

Version Number:

7

Version Date:

07Dec2023

Template No.: CS TP BS016 Revision 6

Reference: CS WI BS005

Effective Date: 02Dec2019

(in Section 16.2.3.2) and CDR-SB (in Section 16.2.3.1) applied to subjects who are asymptomatic at baseline for the All Gant Exposure mITT and main set controls.

The following subset of analyses will be conducted separately for baseline asymptomatic and baseline symptomatic subjects, except where noted for select imaging and fluid biomarker analyses, at the interim analysis and additional exploratory analyses will be conducted as needed, noting that focus will be on Year 2 findings in the absence of Year 3 findings, with any imputation for Year 3 excluded. These analyses will be conducted for the each of the three mITT populations and controls as specified for each model, unless the associated section describes the analysis as being conducted on select mITT populations, noting that when multiple models are described within a section, only the first one will be conducted for the interim unless otherwise specified. By-visit descriptive statistics during OLE will be displayed, overall and by OLE baseline symptomatic status, for each associated parameter, including each component of the OLE cognitive composite.

[REDACTED] [REDACTED]

Author: [REDACTED]

Version Number: 7

Version Date: 07Dec2023

Template No.: CS_TP_BS016 Revision 6

Reference: CS_WI_BS005

Effective Date: 02Dec2019

Table B: Interim Analysis Models

Endpoint	Analysis Tier and Statistical Method	Objective
CDR Global	Primary: 16.2.3.2: Cox proportional hazards time to first progression	To evaluate whether the treatment delays the disease progression
	Sensitivity: 16.2.4.2 (third paragraph): post-baseline PiB-PET SUVR normal	To evaluate whether normal / abnormal amyloid levels are associated with lower risk of first progression (delay of disease progression) in CDR Global compared to all controls
	Sensitivity: 16.2.4.1.1 (third paragraph): comparison to concurrent and non-concurrent controls	To evaluate whether the treatment delays the disease progression in CDR Global compared to the concurrent and non-concurrent controls

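### Counting an unconfirmed CDR rise at the last visit favours whichever group is followed longer; add a confirmed-event sensitivity analysis

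*SAP*

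**What the plan says.** SAP 16.2.3.2 defines CDR Global progression as a rise above baseline "observed at two consecutive measurements unless the progression occurs at the last measurement". It adds: "Subject without progression will be censored at their last measurement". SAP 16.2.3.1 applies the same exception to recurrent CDR-SB progression, which "must be observed at two consecutive measurements unless the progression occurs at the last measurement". Both sections apply the analysis to all three mITT populations against controls.

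SAP 17 makes these two models the primary interim analyses, in "subjects who are asymptomatic at baseline for the All Gant Exposure mITT and main set controls". SAP 5.3 defines that population as "Any subjects treated with Gantenerumab in either DB or OLE who meet mITT criteria using the baseline associated with the first period of Gantenerumab exposure". It therefore contains participants who took double-blind placebo or solanezumab and first received gantenerumab in the OLE (switchers below).

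On the comparator, SAP 5.4.3 says "The main set controls are defined as the external controls plus the internal set controls". On length of follow-up, SAP 5.4 acknowledges an imbalance: "the vast majority of subjects in the controls will represent a shorter duration than seen in subjects within OLE Gant All Gant exposure mITT". That population is restricted to people treated with gantenerumab in both periods, and it is not the interim primary population.

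**The concern.** A confirmation rule presupposes that some CDR rises revert. The exception then gives every participant exactly one visit, the last, at which a transient rise counts. Someone followed for three visits has that chance early and once in three visits; someone followed for eight has it late and once in eight. In a Cox model, the shorter-followed group collects unconfirmed events during years in which the longer-followed group is still subject to confirmation.

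With shorter-followed controls, this lowers the gantenerumab hazard ratio without any drug effect, and the result could not be told apart from a delay in progression. CDR Global and CDR-SB carry the interim question of clinical benefit and are key secondary variables at the final analysis.

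**Working it through.** **Plan's own figure.** None. The documents give no hazard ratio, event count or power for the CDR Cox analyses.

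**Inputs from the documents.** CDR is annual in DIAN-TU (protocol synopsis). The double-blind period lasted 4 to 7 years (protocol 6.3.4) and the OLE up to 3 (SAP 3.1), with Year 2 the focus at the interim (SAP 17). Double-blind carriers numbered 52 gantenerumab, 52 solanezumab and 40 placebo (protocol 3.3). The OLE goal was 60 to 90 of 144 (protocol Appendix 3, 4.1.2).

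**Assumptions.** True conversion λ = 0.05 per year; transient rise with probability q per visit, 0 to 0.10; a 5% miss rate when q > 0; numbers of visits as stated; no drug effect.

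**Hand check, long follow-up against short.** Take gantenerumab at 6-9 visits and controls at 2-4 (mean m = 3). While controls are at risk, no gantenerumab participant has reached a last visit. Two successive transient rises add about q² per year in both groups; only controls add the unconfirmed chance, about q/m per year:

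HR ≈ (λ + q²) / (λ + q² + q/m)

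- q = 0.03: 0.0509 / (0.0509 + 0.0100) = 0.84
- q = 0.05: 0.0525 / (0.0525 + 0.0167) = 0.76
- q = 0.10: 0.0600 / (0.0600 + 0.0333) = 0.64

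With controls at 2-5 visits (m = 3.5), q = 0.03 gives 0.0509 / (0.0509 + 0.0086) = 0.86.

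**Simulated CDR Global null hazard ratios, rule as written** (true value 1.00, Monte Carlo error roughly 0.02-0.04):

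| Gantenerumab visits | Control visits | q = 0 | q = 0.05 | q = 0.10 |
|---|---|---|---|---|
| 6-9 | 2-4 | 1.01 | 0.75 | 0.65 |
| half 6-9, half 2 | 2-4 | 0.98 | 0.91 | 0.85 |
| 40% 6-9, 60% 1-2 | 3-5 | 1.00 | 0.98 | 1.00 |
| 3-5 | 3-5 | 0.99 | 0.99 | 0.99 |
| 2 (switchers only) | 4-6 | 1.01 | 1.48 | 1.68 |

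The first row agrees with the hand check. The last shows the direction reversing.

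**How mixed is All Gant exposure mITT?** If OLE uptake were proportional across arms (an assumption), switchers would number 60 × 92/144 ≈ 38 to 90 × 92/144 ≈ 58, against 52 double-blind gantenerumab participants. Some of those 52 did not continue. A three-part mix (26 continuing with 6-9 visits, 26 double-blind only with 3-6, 38 switchers with 1-2; q = 0.03-0.10) gives 0.83-0.91 against controls with 1-4 visits, 0.92-0.96 against 2-5 and 0.98-1.02 against 2-7. Over all the mixes tried, the range is about 0.81-1.03.

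**False significance favouring gantenerumab** (nominal 2.5%; assumed 40 against 60 participants; q = 0 / 0.05 / 0.10). For 6-9 against 2-4 visits: 1.5% / 6.7% / 15.1%. For the half-and-half mix: 0.7% / 3.0% / 3.7%.

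**Two alternatives, CDR Global, 6-9 against 2-4 visits** (q = 0 / 0.05 / 0.10). Confirmation at every visit with censoring at the penultimate visit: 1.01 / 1.01 / 0.97, with false significance of 1.1-1.9%. Deleting the exception but still censoring at the last visit: 1.55 / 1.58 / 1.50. The last interval then adds time at risk in which no event can be confirmed, and that weighs more on the shorter-followed group.

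**CDR-SB, recurrent gap-time model, 6-9 against 2-4 visits.** The rule's own contribution is the hazard ratio as written divided by the confirmed, penultimate-censored one (q = 0 / 0.05 / 0.10).

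- One step per participant: 0.874/0.895 = 0.98; 0.668/0.862 = 0.78; 0.554/0.821 = 0.67.
- Decline continuing after onset: 2.375/2.751 = 0.86; 1.802/2.413 = 0.75; 1.516/2.205 = 0.69.

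The contribution is toward gantenerumab in both. The total null hazard ratio is below 1 in the first case (0.87 / 0.67 / 0.55) and above 1 in the second (2.4 / 1.8 / 1.5), because longer follow-up collects more repeat events.

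**The case against.** **Population.** A reader might infer from SAP 5.4 that controls are followed for less time in the interim primary comparison, and hence that both interim hazard ratios are biased toward gantenerumab. The documents do not support that. The acknowledgement in SAP 5.4 names OLE Gant All Gant exposure mITT only. All Gant exposure mITT adds switchers with about two OLE years at the interim and double-blind gantenerumab participants who never entered the OLE. For CDR-SB, the sign of the net bias depends on how decline continues. This objection stands and limits the point.

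**Size.** No reversion rate, control follow-up or DIAN-OBS visit interval is given, and with no transient rises CDR Global is unbiased. This also stands. It leaves a range, not a zero: the SAP's own confirmation requirement implies that some reversion is expected.

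**Existing cover.** The CDR-SB linear mixed model, the visit-to-visit logistic model (16.2.4.1.6) and the disease progression models (16.2.4.1.4, 16.2.4.1.5) do not use the rule. They estimate other quantities, however, and none isolates last-visit events. The CDR sensitivity analyses in Table B vary amyloid status and control concurrency. The shared frailty analysis is run only if p is below 0.10 and keeps the same event definition.

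**Timing.** SAP version 7 is dated 07 December 2023, after the 31 March 2023 interim data cut, and its version history says the interim led to early termination of the OLE. Replacing a pre-specified event definition once results are known would invite its own criticism. This stands, and it is why the change proposed is an addition.

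**Conclusion.** The concern holds in conditional form. When some rises are transient, the last-visit exception moves the CDR Global hazard ratio in favour of the longer-followed group. In OLE Gant All Gant exposure mITT, where SAP 5.4 itself says most controls have shorter data, its contribution favours gantenerumab: a null hazard ratio of about 0.65-0.87 at 3-10% transient rises per visit, for assumed 6-9 treated visits against 2-4 or 2-5 control visits. In the interim primary population the effect is smaller, about 0.81-1.03 under assumed mixes, and neither its size nor its direction is fixed by the documents. For CDR-SB the rule's own contribution has the same direction, with net bias not established. No planned analysis would show how much of a result rests on unconfirmed last-visit rises. This is a cheap improvement, not a reason to replace the primary analysis.

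**What to change.** Keep the pre-specified rule as primary. Add to SAP 16.2.3.1 and 16.2.3.2, for all three mITT populations, a sensitivity analysis that:

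- requires two consecutive elevated measurements at every visit, with the last visit used only to confirm;
- censors participants without confirmed progression at their penultimate measurement (for CDR-SB, this applies to the final interval after any confirmed progression);
- is applied identically to gantenerumab and to every control set.

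Report by group the follow-up time, CDR visit spacing and the share of events that are unconfirmed last-visit rises. Do not simply delete the exception while still censoring at the last visit, which biases against the longer-followed group. For CDR-SB, present the result as showing the effect of the last-visit rule alone; it does not remove other biases of the recurrent-event model.

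The cost is one extra derivation and a short table. The sensitivity analysis has fewer events (about 25-40% of treated events lost in the assumed mixed populations). Participants with only one post-baseline CDR do not contribute (about 14-21% of treated participants in those mixes), and these are mainly switchers.
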